#### 285 ***Study Procedures***

286 Prior to randomization, patients will be asked to complete a baseline assessment. This will  
287 consist of baseline demographics including cardiovascular comorbidities, use of cigarettes, and education  
288 level (15). The Morisky 8-item adherence scale will also be collected, which has been validated to  
289 accurately capture anti-hypertensive medication adherence by self-report (8). Baseline hypertension  
290 knowledge will also be assessed in accordance with Oliveira et. al (16). Subjects will also be asked to  
291 complete the Consumer Health Activation Index (CHAI) as a marker for patient activation, as developed  
292 by Wolf et al. Blood pressure monitors will then be mailed after the patients complete the baseline  
293 assessment.

294 Patients assigned to the intervention arm will be emailed with instructions to download the  
295 Medisafe application. Through an integration with Medisafe, Evidation Health will confirm that the  
296 application has been downloaded and launched at least once within two days from randomization.  
297 Patients who do not download and launch the application at least once within two days will be contacted  
298 by email two more times and provided the instructions for download until they launch the application. If

299 they still do not launch the application, they will be contacted twice via telephone, then one final time by  
300 email. If after three reminder e-mails and two phone calls the participant still does not launch the  
301 application, they will not be contacted further about downloading the application, but they will remain in  
302 the intent-to-treat analysis group.

303 Patients assigned to the control arm will not receive any intervention.

304 At two time points, four and eight weeks after randomization, all subjects assigned to intervention  
305 and control will be e-mailed and asked to measure their blood pressure using the Bluetooth-enabled blood  
306 pressure cuff and its associated smartphone application (all blood pressures will be done via two  
307 measurements, taken at least five minutes apart, and averaged (7)). If there is no blood pressure  
308 measurement received within 2 days after the intended upload date, there will be two reminder e-mails  
309 sent until a blood pressure measurement is received. If there is still no blood pressure measurement  
310 received, two phone calls will be made to the study participant, followed by one final email reminder. If  
311 they are unable to be reached by three reminder e-mails and two phone calls, they will not be contacted  
312 again for that blood pressure measurement, but will be contacted to obtain the next assessment (either 8-  
313 week blood pressure measurement or study exit assessment) and will remain in the intent-to-treat analysis  
314 group.

315 At 12 weeks, all subjects will be asked to complete an exit questionnaire consisting of Morisky 8-  
316 item medication adherence scale (8), hypertension knowledge questionnaire (16), and a CHAI. They will  
317 also be asked to take their final blood pressure measurement. The same protocol described above of three  
318 reminder e-mails and two phone calls will be followed, with one additional reminder email (for a  
319 sequence of 2 reminder emails, 2 phone calls, 2 reminder emails), should there be a delay in answering  
320 the questionnaire or taking the blood pressure measurement. Subjects who do not complete the exit  
321 questionnaire or take their final blood pressure measurement will be lost to follow-up. After completing  
322 the study, subjects will be given the option to keep the blood pressure cuff or donate it to an organization  
323 that recycles digital health and wellness products for underserved populations.

324           Subjects may choose to take blood pressure measurements using the Bluetooth-enabled blood  
325   pressure cuff more often than the four readings required in the study. That data will also be transmitted to  
326   Evidation Health via the API and stored in the study database.

327           Throughout the study, subject data including blood pressure measurements and survey data will  
328   be reviewed to ensure data quality and consistency. Patients may be contacted by phone or email to  
329   address suspicious or unusual data submissions.

330           All study subjects will be provided compensation for their time to participate in the study, staged  
331   in four intervals throughout the study (i.e., after randomization, after submitting blood pressure  
332   measurement at 4 and 8 weeks after enrollment respectively, and after completion of final blood pressure  
333   measurement and exit questionnaire). Maximum total compensation per study subject will not exceed  
334   \$150.

335

336   ***Data Security and Confidentiality***

337           All identifiable information about patients, their medical conditions, and other study data will be  
338   secured by Evidation Health in accordance with all local and state laws, regulations and Human Subjects  
339   Committee policies regarding collection and distribution of patient information. Evidation Health will use  
340   a HIPAA compliant survey system to collect the participant information and consent. Participant  
341   information received from smartphone applications will be transmitted using Transport Layer Security  
342   (TLS).

343           Data will only be stored electronically. All PHI and PII will be stored only on a single secured  
344   server in the Amazon EC2 cloud designed exclusively for this purpose. The server will be protected by  
345   two-factor authentication (requiring a password and a code generated on a separate device that changes  
346   every 60 seconds). All communication with the server will be encrypted using TLS. Only Evidation

347 Health's VP of Engineering and Head of Operations will have access to server. Data will be encrypted at  
348 rest.

349 De-identified data will be stored on a separate password-secured server with data at rest  
350 encryption. Only Evidation Health's Head of Operations and Data Science and Data Engineering teams  
351 have access to this server. Only de-identified data will be transferred to the Center for Healthcare  
352 Delivery Science (C4HDS) at Brigham Women's Hospital. Questionnaire data and other de-identified  
353 data will only be linked to PHI and PII through a unique study-generated identifier. This identifier will be  
354 generated via a secure cryptographic hash that cannot be reverse-engineered.

355

#### 356 ***Outcomes***

357 The study's co-primary outcomes will be a change in blood pressure from randomization to three  
358 months later and self-reported medication adherence (see Table 1). The secondary outcome will be  
359 change in number of subjects who have well controlled blood pressure (<140/90 mmHg).

360

#### 361 ***Analytic Plan***

362 The Center for Healthcare Delivery Science (C4HDS) at Brigham Women's Hospital will  
363 conduct all analysis on de-identified data. Analyses will be performed by an intent-to-treat basis, where  
364 subjects will be analyzed in the groups they are assigned to during randomization.

365 We will begin by comparing the baseline patient characteristics in each of the arms using t-tests,  
366 chi-square tests or their non-parametric analogues, as appropriate. We will evaluate for rates of missing  
367 data between the two study arms to ensure that it is non-differential.

368 We will use linear regression to assess the impact of Medisafe on the study's 2 primary outcomes  
369 (change in blood pressure and self-reported adherence) between the two study groups. Our null

370 hypothesis will be that there is no difference in the change in blood pressure between the two groups after  
371 12 weeks.

372 Our primary models will adjust for unbalanced covariates between the two groups (i.e. age,  
373 gender, ethnicity, BMI, comorbidities, number of antihypertensive medications, total number of  
374 medications, education, exercise level, cell phone use) should any exist using a p-value threshold of 0.05  
375 and will impute missing outcome data where 12 week outcome data is unavailable. Imputation will be  
376 performed using the PROC MI command in SAS and will include the covariates defined above as well as  
377 intermediate outcomes (i.e. blood pressure at weeks 4 and 8). Multiple imputation with 5 imputations  
378 will be used and the imputed values will be inspected to ensure in-range values. After imputation,  
379 analyses will be conducted on the imputed data set and the results will be combined using the standard  
380 rules from Rubin et al. In sensitivity analyses, we will analyze only those subjects for whom we have  
381 complete outcome data (i.e. a complete case analysis).

382 In secondary analyses, we will determine the number of patients that had their hypertension  
383 controlled (i.e., <140/90mmHg) during the study period in both arms, and calculate an odds ratio using  
384 multivariate logistic regression with covariates indicated above. In supplemental analyses, we will repeat  
385 our analyses with longitudinal modeling methods that incorporate blood pressure readings at 4, 8, and 12  
386 weeks after randomization. This will be done using generalized estimating equations to account for  
387 correlations between repeated blood pressure readings for any individual subjects. If there are additional  
388 blood pressure readings from patients who took their blood pressure more often than required, the  
389 longitudinal models will be re-run to include these additional values.

390 In subgroup analyses, we will evaluate whether the impact of Medisafe differed for subjects who  
391 interacted with Medisafe frequently (defined as being in the upper median of use for the Medisafe  
392 application based on number of days logged in during the study period) as compared to subjects who  
393 interacted with Medisafe less frequently. We will perform this analysis by including categorical variables  
394 for high and low use in our outcome model, whereby control subjects are indicating by null values for

395 both indicators. We will also evaluate effect modification by hypertension knowledge (16) recorded at  
396 baseline.

397

398 ***Sample Size***

399 With a change in blood pressure of 5mmHg, which has previously been shown to be clinically  
400 significant (12,13), a standard deviation of 16.7mmHg, a power of 80%, and an alpha of 0.05 there would  
401 need to be 312 patients enrolled. With allowance for 20% loss to follow-up, the study will seek to enroll  
402 390 patients total to have an 80% power with an alpha of 5%. With a standard deviation of 1.6 (8) and a  
403 sample size of 390 patients, we will be able to detect a 0.5 Morisky score difference between the groups  
404 with a power of 87%.

405

406 ***Risks Associated with the Intervention***

407 Since the intervention under investigation is not aimed at altering a patient's treatment, but rather  
408 to promote adherence to treatments that they have already been prescribed, the risk will be minimal.  
409 There is a possible risk of patients receiving escalating anti-hypertensive medications from their treatment  
410 team due to non-adherence, and with the better adherence through Medisafe reminders there could be  
411 medication induced hypotension. During the informed consent process and on the blood pressure  
412 measurement guidance sheet there will be recommendations to reach out to their treatment team if they  
413 ever have a blood pressure > 180/120 mmHg or < 90/50 mmHg. The informed consent will also clearly  
414 state that no component of the study, including the home blood pressure cuff use and study personnel, is a  
415 replacement for care from a health care professional.

416 The likelihood that a study participant has a blood pressure reading > 180/120 mmHg or < 90/50  
417 mmHg during the study is very low, since this is a low-risk patient population. Inclusion criteria is limited

418 to patients with stage I or II hypertension, and patients with an initial blood pressure reading > 180/120  
419 mmHg will be excluded. Patients taking more than three anti-hypertensive medications will also be  
420 excluded. Additionally, patients will be notified during the informed consent process that their blood  
421 pressure readings will not be monitored by the research team, and that they should reach out to their  
422 treatment team if their blood pressure is ever very high or very low.

423

424 Summary of changes to protocol

425

Date of submission	Description of modification	Rationale for modification
	Changes in inclusion criteria as follows. Initial: 
 
• <math>\geq 18</math> and <math>\leq 75</math> years of age
 
• Self-reported systolic blood pressure <math>\geq 140</math> mmHg
 
• Systolic blood pressure <math>\geq 140</math> mmHg (+/- diastolic blood pressure <math>\geq 90</math> mmHg), but blood pressure <math>\leq 180/120</math> mmHg confirmed by home BP-cuff
 
 Final: 
 
• <math>\geq 18</math> years of age
 
• Self-reported blood pressure <math>\geq 140/90</math> mmHg
 
• Blood pressure <math>\geq 140/90</math> mmHg, but <math>\leq 180/120</math> mmHg confirmed by home BP-cuff
 
	Removed restriction to individuals $\leq 75$ years of age and clarifying poorly-controlled BP as being defined based on both systolic and diastolic BP
	Addition to exclusion criteria of current use of an automated home blood pressure cuff	Required patients to not currently be using home blood pressure monitors to standardize outcome evaluation
	Change in primary outcome as follows. Initial: 
 
• Change in systolic blood pressure from randomization to three months later
 
 Final: 
 
• Change in blood pressure from randomization to three months later
 
	To reflect the updated inclusion/exclusion criteria

426

427 For a description of changes to the analytic plan, see sections below.

428

429 Initial analytic plan

430 *Analytic Plan*

431 The Center for Healthcare Delivery Science (C4HDS) at Brigham Women’s Hospital will  
432 conduct all analysis on de-identified data. We will report baseline patient characteristics and evaluate  
433 differences in the two groups to identify any potentially unmatched covariates despite randomization. We  
434 will plot changes in blood pressure over time.

435 Analyses will be performed by an intent-to-treat basis, where subjects will be analyzed in the  
436 groups they are assigned to during randomization. We will use linear regression to assess the impact of  
437 Medisafe on the study’s 2 primary outcomes (change in systolic blood pressure and self-reported  
438 adherence) between the two study groups, 3 months after randomization. Our primary models will adjust  
439 for unbalanced covariates between the two groups. Only the initial and 12-week blood pressure readings  
440 will be included in the primary analysis.

441 In secondary analyses, we will determine the number of patients that had their hypertension  
442 controlled (i.e., <140/90mmHg) during the study period in both arms, and calculate an odds ratio using  
443 multivariate logistic regression in order to control for potentially unmatched baseline covariates. We will  
444 also repeat our analyses with longitudinal modeling methods that incorporate blood pressure readings at  
445 4, 8, and 12 weeks after randomization. If there are additional blood pressure readings from patients who  
446 took their blood pressure more often than required, we will include this data in exploratory longitudinal  
447 modeling analyses.

448 In supplemental analyses, we will evaluate whether the impact of Medisafe differed for subjects  
449 who interacted with Medisafe frequently (defined as being in the upper median of use for the Medisafe  
450 application based on frequency of user sessions during the study period) as compared to subjects who  
451 interacted with Medisafe less frequently. We will perform this analysis by including categorical variables  
452 for high and low use in our outcome model, whereby control subjects are indicating by null values for

453 both of these indicators. We will also evaluate effect modification by hypertension knowledge (16)  
454 recorded at baseline.

455

456 *Sample Size*

457 With a change in systolic blood pressure of 5mmHg, which has previously been shown to be  
458 clinically significant (12,13), a standard deviation of 17.6mmHg, a power of 80%, and an alpha of 0.05  
459 there would need to be 312 patients enrolled. With allowance for 20% loss to follow-up, the study will  
460 seek to enroll 390 patients total to have an 80% power with an alpha of 5%. With a standard deviation of  
461 1.6 (8) and a sample size of 390 patients, we will be able to detect a 0.5 Morisky score difference between  
462 the groups with a power of 87%.

463

464 Final analytic plan

465 *Analytic Plan*

466 The Center for Healthcare Delivery Science (C4HDS) at Brigham Women's Hospital will  
467 conduct all analysis on de-identified data. Analyses will be performed by an intent-to-treat basis, where  
468 subjects will be analyzed in the groups they are assigned to during randomization.

469 We will begin by comparing the baseline patient characteristics in each of the arms using t-tests,  
470 chi-square tests or their non-parametric analogues, as appropriate. We will evaluate for rates of missing  
471 data between the two study arms to ensure that it is non-differential.

472 We will use linear regression to assess the impact of Medisafe on the study's 2 primary outcomes  
473 (change in blood pressure and self-reported adherence) between the two study groups. Our null  
474 hypothesis will be that there is no difference in the change in blood pressure between the two groups after  
475 12 weeks.

476 Our primary models will adjust for unbalanced covariates between the two groups (i.e. age,  
477 gender, ethnicity, BMI, comorbidities, number of antihypertensive medications, total number of  
478 medications, education, exercise level, cell phone use) should any exist using a p-value threshold of 0.05  
479 and will impute missing outcome data where 12 week outcome data is unavailable. Imputation will be  
480 performed using the PROC MI command in SAS and will include the covariates defined above as well as  
481 intermediate outcomes (i.e. blood pressure at weeks 4 and 8). Multiple imputation with 5 imputations  
482 will be used and the imputed values will be inspected to ensure in-range values. After imputation,  
483 analyses will be conducted on the imputed data set and the results will be combined using the standard  
484 rules from Rubin et al. In sensitivity analyses, we will analyze only those subjects for whom we have  
485 complete outcome data (i.e. a complete case analysis).

486 In secondary analyses, we will determine the number of patients that had their hypertension  
487 controlled (i.e., <140/90mmHg) during the study period in both arms, and calculate an odds ratio using

488 multivariate logistic regression with covariates indicated above. In supplemental analyses, we will repeat  
489 our analyses with longitudinal modeling methods that incorporate blood pressure readings at 4, 8, and 12  
490 weeks after randomization. This will be done using generalized estimating equations to account for  
491 correlations between repeated blood pressure readings for any individual subjects. If there are additional  
492 blood pressure readings from patients who took their blood pressure more often than required, the  
493 longitudinal models will be re-run to include these additional values.

494 In subgroup analyses, we will evaluate whether the impact of Medisafe differed for subjects who  
495 interacted with Medisafe frequently (defined as being in the upper median of use for the Medisafe  
496 application based on number of days logged in during the study period) as compared to subjects who  
497 interacted with Medisafe less frequently. We will perform this analysis by including categorical variables  
498 for high and low use in our outcome model, whereby control subjects are indicating by null values for  
499 both indicators. We will also evaluate effect modification by hypertension knowledge (16) recorded at  
500 baseline.

501

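### The listed imputation inputs leave out randomised arm and the baseline outcomes; if PROC MI is run on that list, omitting arm shrinks both primary effects toward zero

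*Supplement*

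**What the plan says.** The Analytic Plan section reads the same in the final protocol and in the final analytic plan.

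- **Outcomes analysed:** linear regression on two primary outcomes ("change in blood pressure and self-reported adherence) between the two study groups. Our null").
- **What is imputed:** the primary models adjust for imbalance "and will impute missing outcome data where 12 week outcome data is unavailable. Imputation will be".
- **Inputs to the imputation:** "performed using the PROC MI command in SAS and will include the covariates defined above as well as" "intermediate outcomes (i.e. blood pressure at weeks 4 and 8). Multiple imputation with 5 imputations".
- **The covariates referred to:** "Our primary models will adjust for unbalanced covariates between the two groups (i.e. age", then "gender, ethnicity, BMI, comorbidities, number of antihypertensive medications, total number of", then "medications, education, exercise level, cell phone use) should any exist using a p-value threshold of 0.05". That is ten items. None is randomised arm, baseline BP or baseline Morisky.
- **Sensitivity analysis:** only patients with "complete outcome data (i.e. a complete case analysis").

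No sentence says that imputation is run separately by arm. Under Study Procedures in the final protocol, the Morisky scale is collected at baseline and at 12 weeks only, so it has no week-4 or week-8 value.

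**The concern.** The regression that estimates the treatment effect contains arm. An imputation model without arm draws missing values as if both groups followed one distribution, given the other inputs. Imputed patients then show no arm difference except what their week-4 and week-8 BP carries. For Morisky nothing listed carries it. Averaging these patients with the observed ones dilutes the effect. The between-imputation variance also adds uncertainty that the diluted estimate does not have, so the Rubin standard error is too large. Both errors act against finding a benefit, and both fall on the two co-primary outcomes.

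The missing baseline outcomes are a different matter. They are probably among the best available predictors of the 12-week values. Leaving them out loses precision and makes missing at random harder to defend.

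**Working it through.** **Inputs from the documents** (final analytic plan, Sample Size): 390 randomised; 20% planning allowance for loss to follow-up; Morisky SD 1.6 and difference 0.5; BP difference 5 mmHg and SD 17.6; 5 imputations. Allocation is 1:1 (final protocol), so 195 per arm.

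**Assumptions not in the documents:** two-sided alpha 0.05; missingness completely at random at exactly 20%; within-patient BP correlation 0.3 to 0.7; two time courses for the BP effect; Morisky baseline correlation 0.5.

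**1. The plan's own figures.** 312 / 0.80 = 390. Morisky: SE = 1.6 x sqrt(2/195) = 0.162; 0.5 / 0.162 = 3.086; power = Phi(3.086 - 1.960) = 0.870, the stated 87%. That assumes all 390 scores are observed. With 156 per arm observed, SE = 1.6 x sqrt(2/156) = 0.181 and power is 0.788. The imputed analysis should be judged against this second figure.

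**2. Morisky by hand, arm omitted, 20% missing** (156 observed and 39 imputed per arm).

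- Expected estimate: 0.80 x 0.50 + 0.20 x 0 = 0.40.
- Within-imputation variance: U = 2 x 1.6^2 / 195 = 0.02626.
- Between-imputation variance: B = (0.20 x 1.6 x sqrt(2/39))^2 = 0.0725^2 = 0.00525.
- Rubin SE: sqrt(U + 1.2 x B) = sqrt(0.03256) = 0.180.
- True SE of the estimate: sqrt((0.80 x 0.181)^2 + B/5) = sqrt(0.02101 + 0.00105) = 0.149.
- Power: Rubin df = 4 x (1 + U/(1.2 x B))^2 = 107, critical t = 1.982, threshold 1.982 x 0.180 = 0.358; Phi((0.40 - 0.358) / 0.149) = about 0.61.

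**3. Morisky by simulation** (Bayesian normal regression imputation, 5 imputations, Rubin's rules, 1,500 trials per row). Only the imputation model changes; the analysis model stays the same.

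| Imputation model | Mean estimate (true 0.50) | Power |
|---|---|---|
| no arm, no baseline | 0.40 | 62% |
| baseline, no arm | 0.40 | 62% |
| arm, no baseline | 0.50 | 75% |
| arm and baseline | 0.51 | 79% |

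A second simulation gave 78% for the last row. Without arm, the simulated Rubin SE averaged 0.181 against an empirical SE of 0.148 to 0.150, as in step 2. With arm the two agree (0.184 and 0.187). Rows 2 and 3 isolate the cause of the shrinkage, which is arm and not baseline.

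**4. Dependence on missingness** (4,000 trials per setting). At 10% missing, the Morisky estimate is 0.45 with power 76% without arm, and 0.50 with 83% with arm. At 30%, it is 0.35 with 41% without arm, and 0.50 with 67% with arm.

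**5. BP by simulation** (true effect -5, SD of change 17.6, 20% missing at week 12, 1,000 trials per setting; ranges cover correlations 0.3, 0.5 and 0.7).

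| Imputation model | Effect builds linearly | Full effect from week 4 |
|---|---|---|
| weeks 4 and 8 observed, no arm, no baseline | -4.2 to -4.4 | -4.4 to -4.8 |
| weeks 4 and 8 and baseline, no arm | -4.2 to -4.3 | -4.4 to -4.6 |
| no week-4/8 readings, no arm, no baseline | -3.9 to -4.0 | -4.0 to -4.1 |
| weeks 4 and 8, arm and baseline | -4.9 | -4.9 to -5.2 |

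Power is 57% to 67% in the first row and 69% to 74% in the last. With weeks 4 and 8 observed, the loss is therefore about 5% to 16% of the effect. Without them it approaches the 20% given by 5 x 0.80 = 4.0.

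**The case against.** The strongest reply is that the plan says what the imputation will include and never says that arm is left out. The programmed model may contain it, so bias in the final estimate is not established. That stands, and the point is conditional for this reason. But the plan names covariates, intermediate readings, software and number of imputations without naming arm. PROC MI uses only the variables it is given, so a programmer working from this text would omit arm.

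Other replies stand in part.

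- **Direction.** The error is conservative: simulated rejection under the null was 2.3%. There is no added false-positive risk; the risk is a missed or understated benefit.
- **Other planned analyses.** Complete case is free of this bias when data are missing completely at random (simulated Morisky 0.49, BP -4.8 to -5.1). Longitudinal models using weeks 4, 8 and 12 are planned for BP. These could reveal a discrepancy, but they are sensitivity and supplemental analyses, and a gap from the primary result might be mistaken for informative dropout.
- **Covariate list.** It can be read as the full fixed list or as only those items that prove unbalanced. The text does not settle which.

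A reader might infer that a fifth of the data will be imputed. The documents do not support that, since 20% is a planning allowance. A reader might also set 62% against the stated 87% and blame imputation for the whole gap. But 87% assumes complete data, and 79% is the figure with 312 observed. Morisky power of about 86% to 87% is reached after 20% loss only if baseline Morisky also enters the analysis model, which is a separate choice.

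**Conclusion.** The point holds in conditional form. The plan's list of imputation inputs omits randomised arm, and running PROC MI on that list would bias both primary estimates toward zero with an inflated standard error. For Morisky the expected loss equals the missing fraction. At 20%, 0.50 becomes 0.40 and power is about 62%, some 13 to 17 points below the 75% to 79% reached when only the imputation model is corrected. For BP the loss is smaller where weeks 4 and 8 are observed (-4.2 to -4.8) and close to 20% where they are not (about -4.0).

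These sizes rest on the assumptions listed in the working. The direction rests only on arm being absent while the true effect is not zero and is not fully carried by the other inputs. It would be wrong to attribute the shrinkage to the missing baseline outcomes, because adding baseline without arm leaves the Morisky estimate at 0.40.

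Five imputations is not an error: 50 instead of 5 raised simulated power only from 83% to 85%. The absence of a sensitivity analysis that departs from missing at random is a matter of good practice.

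**What to change.** In the Analytic Plan section of both the final protocol and the final analytic plan, state that PROC MI always includes randomised arm (or is run separately by arm), baseline BP, baseline Morisky, week-4 and week-8 BP and the full fixed covariate list, whether or not any covariate proves unbalanced. If arm was always intended, the same sentence settles it. The cost is one sentence of wording and negligible computing time. No data collection changes, since every variable named is already gathered.

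Optional good practice: use 20 or more imputations with a recorded seed, and add a delta-adjusted run by arm beside the complete-case analysis.
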